## **9. Correlative/Special Studies**

Not applicable.

## **10. Measurement of Effect**

### **10.1 Response Criteria**

Not applicable.

### **10.2 Duration of Response**

Not applicable.

### **10.3 Progression-Free Survival**

Not Applicable.

### **10.4 Other Response**

#### **Parameters**

Not Applicable.

## **11. Data Reporting / Regulatory Considerations**

### **11.1 Data Collection**

The data collection plan for this study is to utilize REDCap to capture all treatment, toxicity, efficacy, and adverse event data for all enrolled subjects.

#### **11.1.1 REDCap**

REDCap (Research Electronic Data Capture) is a free data management software system that is fully supported by the Weill-Cornell Medical Center CTSC. It is a tool for the creation of customized, secure data management systems that include Web-based data-entry forms, reporting tools, and a full array of security features including user and group based privileges, authentication using institution LDAP system, with a full audit trail of data manipulation and export procedures. REDCap is maintained on CTSC-owned servers that are backed up nightly and support encrypted (SSL-based) connections. Nationally, the software is developed, enhanced and supported through a multi-institutional consortium led by the Vanderbilt University CTSA.

### **11.2 Regulatory Considerations**

#### **11.2.1 Institutional Review Board/Ethics Committee Approval**

As required by local regulations, the Investigator will ensure all legal aspects are covered, and approval of the appropriate regulatory bodies obtained, before study initiation.

Before initiation of the study at each study center, the protocol, the ICF, other written material given to the patients, and any other relevant study documentation will be submitted to the appropriate Ethics Committee. Written approval of the study and all relevant study information must be obtained before the study center can be initiated or the IP is released to the Investigator. Any necessary extensions or renewals of IRB approval must be obtained for changes to the study, such as amendments to the protocol, the ICF, or other study documentation. The written approval of the IRB together with the approved ICF must be filed in the study files.

The Investigator will report promptly to the IRB any new information that may adversely affect the safety of the patients or the conduct of the study. The Investigator will submit written summaries of the study status to the IRB as required. On completion of the study, the IRB will be notified that the study has ended.

All agreed protocol amendments will be clearly recorded on a protocol amendment form and will be signed and dated by the original protocol approving signatories. All protocol amendments will be submitted to the relevant institutional IRB for approval before implementation, as required by local regulations. The only exception will be when the amendment is necessary to eliminate an immediate hazard to the trial participants. In this case, the necessary action will be taken first, with the relevant protocol amendment following shortly thereafter.

Once protocol amendments or consent form modifications are implemented at the lead site, Weill Cornell Medicine, updated documents will be provided to participating sites, as applicable. Weill Cornell Medicine must approve all consent form changes prior to local IRB submission.

An IND, including relevant study documentation, will be submitted to the FDA, according to national requirements, for review and approval before the beginning of the study. On completion of the study, the FDA will be notified that the study has ended.

### **11.2.2 Ethical Conduct of the Study**

The Investigators and all parties involved should conduct this study in adherence to the ethical principles based on the Declaration of Helsinki, GCP, ICH guidelines and the applicable national and local laws and regulatory requirements.

This study will be conducted under a protocol reviewed and approved by the applicable ethics committees and investigations will be undertaken by scientifically and medically qualified persons, where the benefits of the study are in proportion to the risks.

### **11.2.3 Informed Consent**

The investigator or qualified designee must obtain documented consent according to ICH- GCP and local regulations, as applicable, from each potential subject or each subject's legally authorized representative prior to participating in the research study. Subjects who agree to participate will sign the approved informed consent form and will be provided a copy of the signed document.

The initial ICF, any subsequent revised written ICF and any written information provided to the subject must be approved by IRB prior to use. The ICF will adhere to IRB requirements, applicable laws and regulations.

#### **11.2.4 Compliance with Trial Registration and Results Posting Requirements**

Under the terms of the Food and Drug Administration Modernization Act (FDAMA) and the Food and Drug Administration Amendments Act (FDAAA), the Sponsor-Investigator of the trial is solely responsible for determining whether the trial and its results are subject to the requirements for submission to <http://www.clinicaltrials.gov>. Information posted will allow subjects to identify potentially appropriate trials for their disease conditions and pursue participation by calling a central contact number for further information on appropriate trial locations and trial site contact information.

#### **11.2.5 Record Retention**

Essential documents are those documents that individually and collectively permit evaluation of the study and quality of the data produced. After completion of the study, all documents and data relating to the study will be kept in an orderly manner by the Investigator in a secure study file. Essential documents should be retained for 2 years after the final marketing approval in an ICH region or for at least 2 years since the discontinuation of clinical development of the IP. In addition, all subjects medical records and other source documentation will be kept for the maximum time permitted by the hospital, institution, or medical practice.

### **12. Statistical Considerations**

#### **12.1 Study Design/Endpoints**

This is a randomized, double-blind, placebo-controlled phase II study to examine the efficacy of rimegepant, an orally available competitive inhibitor of the CGRP receptor, in patients diagnosed with psoriasis. Patients in each strata of disease severity as defined by baseline PASI score (<12, or >=12) will be randomized at 1:1 ratio to receive 16-week treatment of either rimegepant or placebo. The primary endpoint includes the percent reduction in PASI score post-treatment measured at week 16 from baseline defined as  $100\% \times (\text{PASI.pre-PASI.post})/\text{PASI.pre}$ . Secondary endpoints include PASI50, an indicator of whether a patient had at least 50% improvement in PASI score at week 16 post-treatment compared to baseline, the reduction (i.e., the difference) in the Investigator's Global Assessment (IGA) score post treatment from baseline, change in Dermatology Quality of Life Index (DQLI) at week 16 post treatment compared to baseline, change in Itch Score post treatment from baseline, and the overall patterns of change in PASI scores, IGA scores and DQLI scores measured longitudinally.

#### **12.2 Sample Size/Accrual Rate**

The primary objective of the study is to examine if patients receive the rimegepant treatment had greater improvement in psoriasis in terms of the primary endpoints compared to patients received the placebo. The primary endpoints include both the percent reduction in PASI score post-treatment from baseline and the change IGA score post-treatment from baseline.

The sample size is determined to ensure adequate power to detect clinically meaningful differences in the co-primary endpoints between the treatment arms. With a sample size of 30 patients (15 per treatment arm), we will have 80% power to detect an effect size as small

as 1.06 using a two-sample t-test at a two-sided significance level of 0.05 for each of the primary endpoint. This level of effect size corresponds to >21% differences in the percent reduction in PASI scores post treatment from baseline between the two treatment arms assuming the standard deviation of the percent reduction in PASI score is about 20% which is likely to be a conservative estimate based on published results from trials in patients with moderate to severe disease. This level of effect size also corresponds to a difference of 0.5 in the change of IGA scores between the two study arms assuming the standard deviation of change is around 0.5. Accounting for a dropout rate of 25% a total of 45 patients will be recruited.

The study expects to accrue 5 patients per month and accrue all study patients within 6-10 months.

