**Secondary Endpoints:**

1. Fifty percent improvement in PASI instrument.
2. IGA instrument score.
3. DLQI instrument score.
4. Itch Score.

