### **1.2.2 Secondary Objectives**

To determine whether treatment of psoriasis with rimegepant significantly improves patient's quality of life as assessed by the Dermatology Quality of Life Index (DQLI), itch score, and IGA instrument, as well as by a 50% improvement according to the PASI instrument.

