### **12.4 Analysis of Endpoints**

#### **12.4.1 Analysis of Primary Endpoints**

The primary endpoint is the week 16 PASI score. We will calculate the percent reduction in week 16 PASI scores post treatment from baseline. Summary statistics in terms mean, standard deviation, median and range or inter-quartile range will be generated for each study arm. Between treatment arm differences will be evaluated using a two-sample t-test or the non-parametric Wilcoxon rank sum test where appropriate. The primary analysis will be carried out on an intention-to-treat basis. Last value carried forward will be used to impute for patients missing week 16 measurements. Per-protocol analysis will also be carried out among patients who are deemed compliant to treatment (defined as at least 75% of doses taken as measured by pill counts) and had both baseline and week 16 measurements will also be carried out using similar statistical methods. P-values less than 0.05 will be considered statistical significant.

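### Section 12.2 makes IGA change a co-primary endpoint with no success rule, while every other section makes PASI the sole primary endpoint and IGA secondary

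*Combined protocol and SAP*

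**What the plan says.** Section 12.2, which justifies the sample size, treats two endpoints as primary:

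- It lists them: "The primary endpoints include both the percent reduction in PASI score post-treatment from baseline and the change IGA score post-treatment from baseline".
- It sizes the trial on both: "The sample size is determined to ensure adequate power to detect clinically meaningful differences in the co-primary endpoints between the treatment arms".
- It gives each the full significance level: "at a two-sided significance level of 0.05 for each of the primary endpoint".
- It converts the effect size of 1.06 separately for PASI (a difference of just over 21 percentage points, SD about 20) and for IGA (a difference of 0.5, SD around 0.5).

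The other sections name one primary endpoint:

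- The summary's primary objective and endpoint, and Sections 1.2.1 and 1.2.4, name PASI only.
- The summary's secondary endpoints include "IGA instrument score". Section 1.2.2 puts IGA among the secondary objectives ("as assessed by the Dermatology Quality of Life Index (DQLI), itch score, and IGA instrument"), and Section 1.2.5 lists it as the second secondary endpoint.
- Section 12.1 says "The primary endpoint includes the percent reduction in PASI score post-treatment measured at week 16 from baseline", and its list of secondary endpoints contains the reduction in the "Global Assessment (IGA) score post treatment from baseline".
- Section 12.4.1 names the week 16 PASI score, in the singular, as the primary endpoint: "We will calculate the percent reduction in week 16 PASI scores post treatment from baseline". IGA is analysed in Section 12.4.2, under secondary endpoints.

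The only significance rule is in Section 12.4.1: p below 0.05. No section gives a testing order, a split of the significance level, or a one-or-both rule.

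**The concern.** The primary endpoint decides what counts as a positive trial, and here two sections give different answers. If PASI and IGA disagree, Section 12.2 leaves the result undefined, while Section 12.4 judges the same data on PASI alone. A reader could not tell whether a success on IGA only was a prespecified primary result or a secondary one.

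The 80% power and the 0.05 level in Section 12.2 are also per-endpoint figures. They describe the trial only if there is one primary endpoint. With two, either the power to succeed on both is lower or the chance of a false success on at least one is higher, and Section 12.2 reports neither.

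**Working it through.** **Inputs from Section 12.2.** 15 per arm; two-sample t-test; two-sided 0.05 per endpoint; effect size d = 1.06; PASI SD 20 points; IGA difference 0.5 and SD 0.5.

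**Input not in the documents.** The correlation between the PASI and IGA outcomes. It is assumed, over a range of 0 to 0.9, with bivariate normal outcomes.

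**1. The plan's own figure.** Power comes from the noncentral t distribution with 2 × 15 − 2 = 28 degrees of freedom and noncentrality d × √(n/2) = 1.06 × √7.5 = 2.90. The result is 80.0%, as stated. The detectable effect size at 80% power is 1.060. For PASI, 1.06 × 20 = 21.2 points, which agrees with the plan.

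**2. The IGA conversion.** 0.5 / 0.5 = 1.00, not 1.06. With noncentrality 1.00 × √7.5 = 2.74, power is 75.3%. For 80% power at SD 0.5 the difference must be 1.06 × 0.5 = 0.53.

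**3. If the co-primary wording is followed.** At correlation 0 the results follow by hand:

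- Exactly one endpoint significant at the design effects: 2 × 0.80 × 0.20 = 32%.
- Both significant: 0.80 × 0.80 = 64%. With IGA at d = 1.00, 0.800 × 0.753 = 60%.
- At least one significant when neither effect exists: 1 − 0.95² = 9.75%.

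For other correlations, pairs of correlated t-tests were simulated: 200,000 trials per setting at 15 per arm, and 100,000 for the required sizes. Small ranges reflect simulation error.

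| Assumed correlation | Exactly one significant (d = 1.06 each) | Either suffices, unadjusted: false-positive rate | Both required: power, d = 1.06 each | Both required: power, IGA d = 1.00 | Evaluable per arm for 80% joint power (IGA d = 1.06 / 1.00) |
|---|---|---|---|---|---|
| 0 | 32% | 9.75% | 64% | 60% | 20 / 21 |
| 0.5 | 23% | 9.1–9.2% | 68–69% | 65% | 19 / 20 |
| 0.9 | 10% | 7.1% | 75% | 72% | 17 / 18 |

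**4. Either suffices, with the level split.** At 0.025 per endpoint and 15 per arm, power per endpoint at d = 1.06 is 70.2% and the detectable effect size is 1.18. Restoring 80% per endpoint takes 19 per arm.

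**The case against.** The strongest reply is that the intended reading is fairly clear. Section 12.4.1 is the operative analysis section; it names PASI in the singular and sets its test, imputation and threshold. All the objectives and endpoint lists agree with it. Section 12.2 looks like leftover wording, and on the majority reading its PASI figures are right. The joint-power and error figures arise only under the minority wording, and neither success rule appears in the documents. The correlation and the normality are assumed, IGA is a clinician-rated score that may be analysed by a Wilcoxon test, and zero correlation between two severity measures in the same patients is an extreme case. This is also a 30-patient pilot.

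Much of this stands. PASI as sole primary is the likely intent, and the figures for two endpoints are conditional and approximate. The IGA conversion is a small matter, since the SD is itself given as approximate.

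It does not remove the contradiction. Section 12.2 carries the co-primary design through several sentences and gives IGA its own detectable difference, and no rule lets a reader set it aside by counting sections. The loose verb in Section 12.1 and the plural heading of Section 12.4.1 do not settle it either, because each section names only PASI as primary. Pilot or not, the protocol sets a powered comparison and a significance threshold, so the endpoint they apply to must be unambiguous.

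**Conclusion.** The concern holds, and the text must be corrected before unblinding. The current sections contradict each other on which result makes the trial positive, and that finding needs no assumption.

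Its size depends on the reading. With PASI as sole primary, the 0.05 level and 80% power stand, provided 15 per arm are analysed. With two primary endpoints at the design effects, they would disagree in about 10% to 32% of trials (d = 1.06 on both). Requiring both gives about 60% to 75% power; accepting either without adjustment gives a false-positive rate of about 7% to 10%. These ranges rest on the assumed correlations and on bivariate normality. The statement that an IGA difference of 0.5 at SD 0.5 corresponds to effect size 1.06 is a minor error and does not affect the PASI sample size.

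**What to change.** **Preferred, consistent with all other sections.** In Section 12.2, remove the co-primary wording and the naming of IGA as primary. State one primary endpoint, percent reduction in PASI from baseline to week 16, tested at two-sided 0.05, and keep IGA secondary as in Section 12.4.2. If the IGA power statement is kept as supporting information, give about 75% power for a difference of 0.5, or 80% for 0.53, at SD 0.5 with 15 per arm. This costs wording only and leaves the PASI sample size unchanged.

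**If IGA is meant to be co-primary.** Say so in Sections 1, 1.2, 12.1 and 12.4 and state the success rule.

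- *Both required:* report joint power. Reaching 80% takes 17 to 21 evaluable patients per arm over the assumed correlations, that is 2 to 6 more per arm; otherwise acknowledge the lower power.
- *Either suffices:* control the overall error rate. Testing each at 0.025, for example, gives 70.2% power per endpoint at d = 1.06 with 15 per arm, or needs 19 per arm for 80%.

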## 1. Protocol Summary

|                                |  |
|--------------------------------|--|
| Full Title:             | A Pilot Study of Rimegepant in Moderate Plaque-type Psoriasis  |
| Short Title:            | Rimegepant for psoriasis   |
| Clinical Phase:         | 2  |
| Principal Investigator: | [name]   |
| Study Description:      | 
This proposal is for a double-blind, placebo-controlled pilot study examining the use of an orally administered small molecule competitive inhibitor of the calcitonin gene-related peptide (CGRP) receptor for the treatment of moderately severe plaque-type psoriasis. We hypothesize that interruption of CGRP signaling will prove beneficial in psoriasis.
  |
| Sample Size:            | N=15 for each of 2 cohorts.  |
| Enrollment:             | The study will enroll 30 subjects and we anticipate screening up to 110 subjects.  |
| Study Population:       | Thirty adults with mild to moderate plaque-type psoriasis who are otherwise generally healthy. Subjects for the study will be 18 to 75 years of age.   |
| Enrollment Period:      | The enrollment period will be approximately 3 years 1 month.   |

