## 8.2 Participant Discontinuation/Withdrawal from the Study

Participants are free to withdraw from participation in the study at any time upon request. An investigator may discontinue or withdraw a participant from the study for the following reasons:

1. Pregnancy. However, subjects will be followed until the end of the pregnancy.
2. Significant study intervention non-compliance (failure to take medications, refuses to allow study procedures).
3. Participant lost to follow-up after 3 attempts to contact subject to schedule study visit.

The reason for participant discontinuation or withdrawal from the study will be recorded on the Case Report Form (CRF). Subjects who sign the informed consent form and are randomized but do not receive the study intervention may be replaced. Subjects who sign the informed consent form, and are randomized and receive the study intervention, and subsequently withdraw, or are withdrawn or discontinued from the study will not be replaced.

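### Section 12.2 recruits 45 while the Protocol Summary enrolls 30, and 45 does not follow from the 30 patients and 25% dropout in its own paragraph (40 does)

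*Combined protocol and SAP*

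**What the plan says.** Section 12.2 (Sample Size/Accrual Rate) gives the base for the power claim: "With a sample size of 30 patients (15 per treatment arm), we will have 80% power to detect an effect size as small". The effect in question is d = 1.06, for a t-test between the two arms with two-sided alpha 0.05, and the claim is made for each primary endpoint. The section converts this effect to more than 21 points of percent PASI reduction at an SD of about 20. It also equates it with a 0.5 difference in IGA change at an SD of about 0.5. The paragraph ends: "Accounting for a dropout rate of 25% a total of 45 patients will be recruited".

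The Protocol Summary (Section 1) gives 30 in three rows:
- The row on enrollment, which counts screening separately, reads "The study will enroll 30 subjects and we anticipate screening up to 110 subjects".
- The row on sample size gives the same total by arm: "N=15 for each of 2 cohorts".
- The row that describes who is studied begins "Thirty adults with mild to moderate plaque-type psoriasis who are otherwise generally healthy".

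On replacement, Section 8.2 says that subjects "randomized but do not receive the study intervention may be replaced", whereas those who are treated and "subsequently withdraw, or are withdrawn or discontinued from the study will not be replaced".

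On missing data, Section 12.4.1 says of the intention-to-treat primary analysis: "Last value carried forward will be used to impute for patients missing week 16 measurements". Section 8.1 adds that patients who stop treatment are still assessed for disease severity to the end of the 20 weeks.

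**The concern.** A reader cannot tell whether enrollment closes at 30 or at 45. The gap is 15 patients, half of the smaller figure. It affects how many people are exposed, the randomization list, the drug supply, and whether the 80% power statement describes the trial that is run. Stopping at 30 falls short of Section 12.2, and continuing to 45 exceeds the Summary.

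The 45 is presented as the result of a dropout adjustment, yet the adjustment described does not produce it. If 30 is the true target, the paragraph expects a quarter of patients to drop out while the enrolled number equals the number on which the power was computed.

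**Working it through.** **Inputs.** From Section 12.2: 30 patients (15 per arm), d = 1.06, two-sided alpha 0.05, two-sample t-test, PASI SD 20, IGA difference 0.5 with SD 0.5, dropout 25%, total 45. From the Protocol Summary: 30 enrolled. Allocation is 1:1 (Section 12.3). Power is P(|T| > t(0.975, n1+n2-2)), where T is noncentral t with noncentrality d x sqrt(n1 x n2/(n1+n2)).

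**Step 1: the base of 30.** At 15/15 and d = 1.06, the noncentrality is 1.06 x sqrt(7.5) = 2.90, the critical value is 2.048 (28 df), and power is 80.0%. The detectable difference is 1.06 x 20 = 21.2 PASI points. The plan's base figure reproduces.

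**Step 2: the total of 45.**
- Usual inflation: 30/(1 - 0.25) = 40.
- Common shortcut: 30 x 1.25 = 37.5, rounded up to 38.
- Dropout implied by going from 30 to 45: 1 - 30/45 = 33.3% (or 50% by the shortcut).
- Working back: 45 x 0.75 = 33.75 completers, not 30.

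The 45 does not reproduce from 30 and 25%.

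**Step 3: could 45 have another base?** The IGA figures in the same paragraph give d = 0.5/0.5 = 1.0, not 1.06. At d = 1.0, power is 75.3% with 15/15, 79.4% with 16/17 and 80.7% with 17/17, so 80% needs 17 per arm, or 34. Then 34/0.75 = 45.3, close to 45. The text does not say that the 45 was reached this way.

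**Step 4: what each total leaves after 25% loss (completers only).**

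| Enrolled | Completers | PASI power, d = 1.06 | IGA power, d = 1.0 |
|---|---|---|---|
| 30 | 22.5 (22-23) | 65.7% (11/11) to 67.8% (11/12) | 60.7% (11/11) to 62.8% (11/12) |
| 40 | 30 | 80.0% (15/15) | 75.3% (15/15) |
| 45 | 33.75 (33-34) | 83.8% (16/17) to 85.0% (17/17) | 79.4% (16/17) to 80.7% (17/17) |

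With 30 enrolled and an uneven loss leaving 9/13, PASI power is 64.3%. The PASI difference detectable with 80% power rises from 21.2 points to 24.5 (11/12) or 25.1 (11/11).

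**Step 5: does anything else settle the total?** The accrual rate of 5 per month over 6-10 months does not: 30/5 = 6, 40/5 = 8 and 45/5 = 9 months all fit.

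**The case against.** **Recruited might mean screened.** This does not reconcile the totals. The Summary gives screening separately as up to 110, and Section 12.2 ties the 45 to dropout.

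**The 45 may come from the IGA endpoint.** This stands in part. Section 12.2 calls IGA change a co-primary endpoint, and its own IGA figures with 25% dropout lead to about 45. So it would go too far to say that 45 is inconsistent with every input in the plan. But the paragraph attaches the 25% to a base of 30, never mentions 34, and claims 80% power at 30 for each primary endpoint. Sections 12.1 and 12.4.2 also treat IGA as secondary.

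**No harm to the primary analysis is shown.** This stands. A reader might infer that enrolling 30 cuts the power of the primary test to about two thirds. The documents do not support that. The primary analysis is intention-to-treat with last value carried forward, and patients who stop treatment are still followed, so 25% dropout need not mean 25% missing week 16 values. Its power at 30 enrolled could be above or below 80%, depending on the effect and variability of the carried-forward values, which are not given. Section 12.6.2, which limits response assessment to patients with at least 4 weeks of treatment, further clouds who is analysed. The completer figures are not exactly the per-protocol analysis either, since that set also requires at least 75% of doses taken.

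**The error is upward, and this is a pilot.** If 45 are enrolled, the stated dropout is more than covered for PASI. That limits the harm but leaves the two totals in conflict, and Section 12.2 makes a formal power claim that needs a definite N.

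**Conclusion.** Wrong as written, and it must be fixed, on two grounds. The enrolled total is 45 in Section 12.2 and 30 in the Protocol Summary. And 45 does not follow from the 30 patients and 25% dropout in its own paragraph: that gives 40, while 45 implies 33.3%. The near match with 34/0.75 = 45.3 is a possible origin that the documents do not confirm.

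If 30 governs, the stated dropout is not provided for. Replacement covers only patients who are randomized but never treated. The completer-only power of about 66-68% for PASI assumes the full 25% have no week 16 value, near-even losses between arms, and the planned effect and SD. It is a sensitivity figure and not an estimate for the primary analysis. The finding rests on the conflicting N and the failed arithmetic, both of which can be read directly from the text.

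**What to change.** State one enrolled N in Sections 1 and 12.2 and show how it follows from the dropout rate. Settle whether IGA is co-primary first, because the N depends on it.

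**If N is 30:** delete the 45 and state that:
- the 80% power is for d = 1.06 (21.2 PASI points at SD 20), with all 30 patients contributing an analysable value and no dropout allowance;
- the 0.5 IGA difference at SD 0.5 (d = 1.0) has about 75% power at 15 per arm;
- as a sensitivity figure only, a comparison of 22-23 completers has about 66-68% power for PASI if losses are near even, and about 64% if they split 9/13.

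**If an inflated target is kept:** give the arithmetic, 30/0.75 = 40 (20 per arm) for the stated base of 30, or name another base and the endpoint it serves. Then change the Summary's 30 and 15 per cohort to match.

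**Cost.** Keeping 30 is wording only, but the stated power becomes less favourable. A target of 40 adds 10 patients to the Summary's figure. Compared with 45, it saves 5 patients but leaves 30 rather than 33-34 expected completers: PASI power 80% against 84-85%, and IGA power 75% against 79-81%.
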